## Primary aims:

- 1. To determine the relationship between adjunct BFR training during post-surgical rehabilitation and isometric and isokinetic lower extremity strength measures (HUMAC isokinetic dynamometer).
  - a. We hypothesize that there will be a positive association between BFR training and isometric and isokinetic lower extremity strength
- 2. To determine the impact of adding BFR training during post-surgical rehabilitation on functional outcomes.
  - a. We hypothesize that BFR training will improve scores on lower extremity functional tests when compared to a control group.

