### **Prospective Control Inclusion Criteria:**

- Patients between the age of 12 and 18 years at the time of surgery.
- Post-primary ACL reconstruction
- Orthopaedic surgical intervention (including all additional procedures at the knee) completed by one of the Elite Sports Medicine physicians.
- Patient completed postoperative rehabilitation following standard protocols
- Patient did NOT use BFR training during their rehabilitation
- Patient did NOT complete physical therapy at Connecticut Children's Sports Physical Therapy.

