## Patient Reported Outcomes:

- 1) 4 Patient reported outcome measures will be collected at 5 time points listed below:
  - a) Pre-operative visit
  - b) 3 months post-operative
  - c) Return to sport testing
  - d) 12 month follow up
  - e) 2 year follow-up over phone or email
- 2) Outcome measures completed:
  - a) International Knee Documentation Committee (IKDC)
  - b) Anterior Cruciate Return to Sport after Injury (ACL-RSI)
  - c) Knee Injury and Osteoarthritis Outcome Score (KOOS)
  - d) Marx Activity Rating Scale (MARX)

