## 4.

## A) Pre-operative visit

- a. Isometric knee extension at 60 degrees on involved and involved side.
  - i. Quadriceps deficit= 100- (Knee extension peak torque involved/knee extension peak torque uninvolved)
- b. Isometric knee flexion at 60 degrees on involved and uninvolved side
  - i. Hamstring Deficit= 100- (Knee flexion peak torque involved/knee flexion peak torque uninvolved)
- c. Isometric hip extension at 60 degrees on involved and uninvolved side
  - i. Hip extension deficit= 100- (Hip extension peak torque involved/hip extension peak torque uninvolved)
- d. Quad hypertrophy will be measured by thigh circumference measurement.
  - i. Measured at 10cm above the superior pole of the patella bilaterally

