### 5. Return to sport testing:

- a. Isometric knee extension at 60 degrees on involved and involved side.
  - i. Quadriceps deficit= 100- (Knee extension peak torque involved/knee extension peak torque uninvolved)
- b. Isometric knee flexion at 60 degrees on involved and uninvolved side
  - i. Hamstring Deficit= 100- (Knee flexion peak torque involved/knee flexion peak torque uninvolved)
- c. Isokinetic knee extension at 300 deg/ sec, 180 deg/sec, and 60 deg/ sec
  - i. Quadriceps deficit= 100- (Knee extension peak torque involved/knee extension peak torque uninvolved)

- d. Isokinetic knee flexion 300 deg/ sec, 180 deg/sec, and 60 deg/ sec
  - i. Hamstring Deficit= 100- (Knee flexion peak torque involved/knee flexion peak torque uninvolved)
- e. Isometric hip extension at 60 degrees on involved and uninvolved side
  - i. Hip extension deficit = 100 (hip extension peak torque involved/ hip extension peak torque uninvolved)
- f. Quad hypertrophy will be measured by thigh circumference measurement.
  - i. Measured at 10cm above the superior pole of the patella bilaterally
- g. Anterior reach test (all measures taken bilaterally)
  - i. 3 trials anterior reach involved and uninvolved (cm)
  - ii. Anterior reach difference= Max anterior reach involved Max anterior reach uninvolved
- h. Single leg heel raise testing (all measures taken bilaterally)
  - i. Maximum number of repetitions completed to maximum height at pace of 60 beats per second
  - ii. Heel raise difference = heel raise involved heel raise non involved
- i. 8" Anterior Stepdown Test (measures taken bilaterally)
  - i. Involved repetitions= Max repetitions in 1 minute.
  - ii. Uninvolved repetitions= Max repetitions in 1 minute.
- j. Half kneeling dorsiflexion (all measures taken bilaterally)
  - i. Half kneeling difference = half kneeling involved- half kneeling non involved
- k. Single leg hop for difference (all measures taken bilaterally)
  - i. Single leg hop difference = maximum involved distance maximum non- involved distance
- 1. Timed hop for distance (all measures taken bilaterally)
  - i. Timed hop difference = time involved time non involved
- m. Single leg triple hop for distance (all measures taken bilaterally)
  - i. Single leg triple hop difference = maximum involved distance maximum non-involved distance
- n. Cross over hop for distance (all measures taken bilaterally)

- o. Cross over hop difference = maximum involved distance maximum non-involved distance

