- 6. 12-month testing

Tegner Activity Scale

- 7. Prospective control: All prospective controls will follow the ACL reconstruction protocol at an outside facility. These patients will complete outcome measures, and standardized strength assessments consistent with the standard current standard of care listed above. The same data points will be collected.
- 8. Retrospective controls: Outcome measures (RSI, IKDC) and the results of standardized 3 and 6mo + assessment results will be collected.
- 9. All data points listed above for all three groups will be stored in a Microsoft Excel spreadsheet on the G drive.

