## Data Analysis:

The endpoint of this study is when data is collected and analyzed from 20 patients who have completed a one year follow up from date of surgery.

Data will be collected on all patients who meet the inclusion criteria for this study and have agreed to participate through the consenting process. Descriptive statistics will be completed to help gain an overall understanding of the data for the effect of BFR training on lower extremity strength, mid-thigh circumference and outcome measures. T-tests between strength and outcome variables for the BFR and non-BFR group to test if there are differences between the two groups. Correlation tests will be used to determine association between lower extremity strength and BFR training. Corrections will be made for multiple comparisons.

We will be entering into a Data Use Agreement with University of Connecticut (UCONN) for assistance with data analysis and interpretation as well as statistical analysis. All data sharing procedures will be in accordance with Connecticut Children's policy. All data will be de-identified prior to sharing to assure patient's confidentiality. The UCONN collaborator is not engaged in human subject research (no access to identifiers) and will obtain an independent determination from the UCONN IRB.

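### The prospective arms are formed by therapy site but compared with unadjusted t-tests, although pre-operative values, age and sex are collected in both

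*Combined protocol and SAP*

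**What the plan says.** Study Design describes 33 patients who have therapy at the study clinic with BFR, and 14 prospective controls who have it elsewhere without BFR. The control criteria make this explicit: "Patient did NOT complete physical therapy at Connecticut" Children's own sports therapy service. No randomisation is described.

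Data Analysis lists descriptive statistics, "T-tests between strength and outcome variables for the BFR and non-BFR group to test if there are differences between the two groups", correlations of strength with BFR training, and one line on multiplicity: "Corrections will be made for multiple comparisons". It names no covariate, regression, change score or stratification. The only confounder control in the document is matching on age, sex, BMI and surgical procedure, and it applies only to the fallback retrospective controls.

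The data needed for adjustment are already planned:
- Age and sex are on the demographic list.
- The pre-operative visit records isometric knee extension, knee flexion ("Isometric knee flexion at 60 degrees on involved and uninvolved side") and hip extension, plus thigh circumference.
- "4 Patient reported outcome measures will be collected at 5 time points listed below", the first being pre-operative: IKDC, ACL-RSI, KOOS and Marx.
- For prospective controls, item 7 of the data-points list says "The same data points will be collected".

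Other outcomes have no pre-operative value. "Isokinetic knee extension at 300 deg/ sec, 180 deg/sec, and 60 deg/ sec" first appears at return-to-sport testing. Y-balance, step-down, bridge, heel raise, dorsiflexion and hop tests start at 3 months or at return to sport.

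**The concern.** The aims are worded as effects. Under Primary aims, for example: "We hypothesize that BFR training will improve scores on lower extremity functional tests when compared to a control group". When arms are formed by where patients go for therapy, nothing balances pre-operative strength, symptoms, age or sex. A t-test on follow-up values attributes part of any such difference to BFR. The error can create an apparent benefit or hide a real one.

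Descriptive statistics may reveal an imbalance, but the plan does not say how the comparison would then allow for it. A decision made after seeing the data would be post hoc. A multiplicity correction lowers the rejection rate but leaves the bias in the estimate unchanged.

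**Working it through.** The documents give no figure to reproduce: the sample size section states no alpha, power, effect size or SD. What follows is an illustration.

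**Inputs from the documents.** Arms of 33 and 14 (Study Design, which also mentions 20 controls).

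**Assumed inputs.** Unit within-arm SD; pre/post correlation ρ = 0.3, 0.5, 0.7; imbalance g = 0.2 or 0.5 SD; no losses; two-sided 5% before any multiplicity correction; t-test on follow-up values.

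**T-test, no BFR effect.**
- SE = √(1/33 + 1/14) = 0.319 SD, with 33 + 14 − 2 = 45 degrees of freedom.
- Bias = ρ × g. At g = 0.5 this is 0.15, 0.25 and 0.35 SD.
- Noncentrality = bias/SE = 0.47, 0.78 and 1.10. Rejection comes from the noncentral t distribution.

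| Setting | ρ = 0.3 | ρ = 0.5 | ρ = 0.7 |
|---|---|---|---|
| 33 v 14, g = 0.2 | 5.4% | 6.1% | 7.1% |
| 33 v 14, g = 0.5 | 7.5% | 12.0% | 18.9% |
| 33 v 20, g = 0.5 | 8.1% | 13.9% | 22.8% |
| 28 v 12 (assumed 15% loss), g = 0.5 | 7.1% | 10.9% | 16.7% |
| 33 v 14, g = 0.5, Bonferroni over eight outcomes (0.05/8 = 0.625%) | 1.2% | 2.4% | 4.6% |

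**ANCOVA: group + baseline covariate + age + sex.** This was simulated with 40,000 trials per cell at 33 v 14 and g = 0.5. The covariate correlates q with the outcome's true baseline, so a fraction 1 − q² of the bias remains: 1 − 0.49 = 51% at q = 0.7, and 1 − 0.25 = 75% at q = 0.5.

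| Covariate | Remaining bias (SD), ρ = 0.3/0.5/0.7 | Rejection, ρ = 0.3/0.5/0.7 |
|---|---|---|
| Own pre-operative value (q = 1) | within 0.002 | 4.9/4.9/5.0% |
| Own value, assumed reliability 0.9 (q² = 0.9) | 0.01/0.03/0.03 | 4.8/5.1/5.2% |
| Proxy, q = 0.7 | 0.08/0.13/0.18 | 5.7/6.7/9.5% |
| Proxy, q = 0.5 | 0.11/0.19/0.26 | 6.1/8.7/13.2% |

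At 0.625%, own-value ANCOVA rejects about 0.6%.

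**Opposite direction.** Assume a true effect of 0.8 SD and an imbalance of 0.5 SD against the BFR arm. T-test power falls from 68.9% (no imbalance) to 51.4/39.3/28.2%. Own-value ANCOVA gives 67.6/75.8/89.7%. The proxies give 57.6/55.2/54.8% at q = 0.7 and 53.3/45.9/39.7% at q = 0.5.

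**Precision with no imbalance.** The mean 95% CI half-width is 0.64 SD for the t-test. It is 0.63/0.57/0.47 SD with the own value, 0.65/0.62/0.58 SD with a proxy at q = 0.7, and 0.66/0.64/0.62 SD at q = 0.5.

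**The case against.** - **Nothing shows that the arms differ.** Both share the age range, primary reconstruction, surgical group and exclusions, and strength is expressed relative to the uninvolved limb. Study Limitations does mention sampling bias, but in terms of power and external validity, so it is weak support for a between-arm imbalance. This stands: the imbalance may be small, and at 0.2 SD the inflation is slight. Shared eligibility still does not balance pre-operative deficit, and limb ratios do not apply to questionnaires.
- **The t-tests might be meant for change scores.** The plan does not say, and the thigh-circumference hypothesis could be read that way. Bias is then (ρ − 1) × g, of opposite sign, and the SD of change is √(2(1 − ρ)). At g = 0.5 the rejection rates are 14.8/12.0/9.1%. The pattern across ρ reverses, but bias remains and the same ANCOVA removes it.
- **This is a pilot meant to inform a later study.** True, and it tempers the severity. Group tests are still planned, and the results are meant to inform surgeons about effectiveness.
- **The final sample may be smaller.** Data Analysis sets the endpoint at 20 patients with one-year follow-up. If that means 20 in total, split 14 v 6 (assumed), the t-test figures at 0.5 SD are 6.0/7.7/10.4%, and a four-term model is less comfortable.
- **BMI and procedure are omitted, though the plan matches retrospective controls on them.** With 14 controls a short list is defensible, but differences in those variables would remain.
- **The fix only partly reaches the primary aims.** Correct: all of Aim 2 and the isokinetic part of Aim 1 have only a proxy, and therapy site is untouched.

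**Conclusion.** The concern holds and should be fixed. The arms are formed by therapy site, the planned comparison has no adjustment, and the variables needed are already collected in both prospective arms. The size depends on imbalance and correlation values that the documents do not give: from near nothing at 0.2 SD imbalance to a bias of 0.15 to 0.35 SD and a 7.5% to 18.9% rejection rate at 0.5 SD. Adjustment corrects this almost fully for eight outcomes and only in part for isokinetic and functional outcomes. It deals with measured differences only and cannot separate BFR from therapy site.

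**What to change.** In Data Analysis:

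1. For isometric knee extension, knee flexion and hip extension, thigh circumference, IKDC, ACL-RSI, KOOS and Marx, replace the t-test in the prospective comparison by ANCOVA with group, the outcome's own pre-operative value, age and sex. Report the adjusted difference with its 95% CI.
2. For outcomes with no pre-operative value (isokinetic strength and the functional tests), adjust for pre-operative isometric quadriceps deficit, age and sex. State that this removes only part of any baseline bias.
3. Report any retrospective-control comparison separately. State that these controls are matched on age, sex, BMI and procedure, were treated at the same clinic in an earlier period, and have no pre-operative strength listed, so baseline-strength adjustment is not available for them.
4. Apply the planned multiplicity correction to the adjusted tests.
5. Describe the results as adjusted associations, and add to Study Limitations that BFR cannot be separated from therapy site in the prospective comparison.

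The cost is wording in Data Analysis and one sentence in Study Limitations. The prospective arms need no new data, the model is an ordinary linear regression, and outside statistical help is already arranged. At 33 v 14 the error degrees of freedom fall from 45 to 42 (47 patients minus five coefficients). Precision gains little or nothing at ρ = 0.3.

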## Study Design

The planned pilot study is a prospective study to compare the use of exercises augmented with BFR with quantitative measurements of strength and patient reported outcomes. A total of 33 youth and adolescent patients undergoing a surgical procedure for ACL reconstruction at Connecticut Children's Elite Sports Medicine and completing physical therapy at Connecticut Children's Sports Physical Therapy will be recruited for this study. Additionally, 14 patients will be recruited that do not participate at Connecticut Children's Sports Physical Therapy and do not receive BFR training as prospective controls. Should we be unable to obtain 20 prospective controls, a review of data from 20 previous patients, matched for age, sex, BMI and surgical procedure that completed physical therapy at Connecticut Children's Sports Physical Therapy will be used as a comparison.

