## Sample Size Justification

It is our intention to use all possible patients meeting the inclusion criteria in this study. According to the most recent clinical data available, approximately 100 patients per year receive care for ACL knee injury and 25 to 50 patients per year receive physical therapy at Elite Sports Medicine following ACL reconstruction.

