## **Data Collection and Management**

a. Data collection forms: All data will be entered into a Microsoft Excel database to facilitate data analysis.

b. Data collection software: Data collection software will include Microsoft Excel to organize data. Statistics will be run using Microsoft Excel.

c. All outcome measures will be completed and stored in a secure online database: Microsoft Excel spreadsheet on G drive.

d. [name] will oversee data management. The data will be collected by investigators, and it will be stored in a secured folder on the G drive. The spreadsheet will only be accessible to those individuals included in this study.

e. Information will be reviewed prior to de-identification to insure there are no errors with transcription.

f. Data quality assurance: Data that is collected will be manually verified to ensure that no information has been entered into Excel incorrectly. Additionally, we will randomly check 10% of data in the Excel data base for accuracy after initial entry to insure accuracy.

CCMC Department of Research

g. Record retention and confidentiality will be dictated by the current procedures in place here at Connecticut Children's. All information will be stored in a private office and on a single password protected computer. No access to information is possible from an outside source.

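### Two-group t-tests with no named visit ignore earlier scores on repeated outcomes, and can bias the comparison if loss is outcome-related and differs by group

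*Combined protocol and SAP*

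**What the plan says.** All references are to the combined protocol and SAP.

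- **Data Analysis** plans descriptive statistics, then "T-tests between strength and outcome variables for the BFR and non-BFR group to test if there are differences between the two groups". It adds "Correlation tests will be used to determine association between lower extremity strength and BFR training" and "Corrections will be made for multiple comparisons". It does not say which visit is tested, whether raw or change scores are used, or what happens to a patient with a missing value.
- **Patient Reported Outcomes:** "4 Patient reported outcome measures will be collected at 5 time points listed below". These are pre-operative, 3 months, return to sport, 12 months, and 2 years by phone or email.
- **Functional Outcome Definitions/Data Points Collected** and the visit lists after it place isometric knee and hip strength at three visits: pre-operative, 3 months and return to sport. Isokinetic strength appears only at return to sport. The 12-month list contains only the Tegner scale.
- **Study Design** gives "A total of 33 youth and adolescent patients undergoing a surgical procedure for ACL reconstruction" for the BFR group, then "Additionally, 14 patients will be recruited that do not participate" at the in-house clinic as controls. The sentence after that speaks of 20 prospective controls, with matched past patients as a fallback.
- **Items 7 and 8, after the 12-month testing list:** prospective controls have their rehabilitation at another facility. For retrospective controls only two questionnaires (RSI, IKDC) and the 3-month and 6-month-plus assessments are listed.
- **Retention** makes attendance at 90% of visits a condition of inclusion.
- **Sample Size Justification** has no dropout allowance: "It is our intention to use all possible patients meeting the inclusion criteria in this study".
- **Data Collection and Management:** "Statistics will be run using Microsoft Excel". Data Analysis separately brings in a university collaborator for statistical work.

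**The concern.** A t-test uses one value per patient. With five questionnaire visits, the analyst must either run several tests or choose one visit. Either way, a patient without that visit's score leaves the comparison, although up to four earlier scores may be on file. Testing change scores does not bring that patient back.

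Loss may well differ between groups. BFR patients attend the in-house clinic, while prospective controls are by definition treated elsewhere and meet the study team mainly at surgeon visits. The last contact is remote. With only 14 prospective controls, a few losses matter. If those who drop out are doing better or worse than those who stay, and this differs between groups, the t-test shows a difference that BFR did not cause.

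**Working it through.** **Nothing to reproduce.** The plan states no power, effect size, SD, loss rate or alpha. The figures below illustrate the risk under stated assumptions.

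**Inputs from the document:** 33 BFR patients, 14 prospective controls, five questionnaire visits.

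**Assumed:** SD 1 at each visit, no true group difference, equal correlation ρ of 0.3 to 0.7 between any two visits, two-sided alpha 0.05. Where loss at 2 years depends on the 12-month score, the log-odds of loss rise by 1.5 for each SD lower. Each case was simulated 6,000 times.

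**When the t-test is biased.** Suppose loss depends only on the 12-month score. Let r be the amount by which the mean 12-month score of retained patients exceeds that of their whole group, in SD. Then

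bias at 2 years = ρ × (r_BFR − r_control).

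This is zero when loss is unrelated to scores, and also when the selection is the same in both groups. Unequal loss alone is not enough.

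**Results** (BFR minus control, higher score better; loss given as BFR v control):

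| Loss pattern | Loss | t-test bias (SD) | Type I error |
|---|---|---|---|
| Unrelated to scores | 10% v 30%, 20% v 40% | within 0.01 | 4.6–5.3% |
| Same dependence in both groups | 20% v 20% | within 0.01 | 4.8–5.2% |
| Same dependence in both groups | 10% v 30%, 20% v 40% | −0.05 to −0.15 | 4.8–6.0% |
| Dependence in controls only | 10% v 30% | −0.10 to −0.23 | 5.9–8.1% |
| Dependence in controls only | 20% v 40% | −0.13 to −0.30 | 6.2–10.7% |
| Dependence in controls only | 10% v 50% | −0.16 to −0.38 | 7.0–13.4% |

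Check against the formula, controls only, 10% v 30%: 0.097/0.3 = 0.32, 0.159/0.5 = 0.32, 0.230/0.7 = 0.33. The implied r is constant, as it should be. The sign here works against BFR, because the controls who stay are the better ones.

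A second simulation (4,000 runs, about 30% missing, correlation 0.6 and 0.75 between 12 months and 2 years) gave 0.14 to 0.18 SD when low scorers were lost from the BFR group only. It gave 0.31 to 0.38 SD when selection ran in opposite directions in the two groups.

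**Using the earlier scores.** The 2-year score was regressed on group and the four earlier scores, and predictions were averaged over all patients. This stands in for a likelihood-based repeated-measures model. Bias fell to within 0.02 SD in every case in the table. That result follows from the assumption that loss depends on an observed score. When control loss depended on the unseen 2-year score (20% v 40%), the t-test bias was −0.43 SD, and −0.17 to −0.35 SD remained after using the earlier scores.

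**Precision.** With SD 1, SE = √(1/n₁ + 1/n₂), and the difference detectable with 80% power is (1.96 + 0.84) × SE.

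- No loss, 33 v 14: SE 0.319, detectable 0.89 SD
- 10% v 30% loss, 29.7 v 9.8: SE 0.368, detectable 1.03 SD
- 20% v 40% loss, 26.4 v 8.4: SE 0.396, detectable 1.11 SD

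Power for 0.8 SD falls from 71% to 58% and 52%. Earlier scores recover part of this. Under random loss at 10% v 30%, the SE fell from 0.373 to 0.368 (1%) at ρ = 0.3, from 0.379 to 0.361 (5%) at 0.5, and from 0.374 to 0.341 (9%) at 0.7. The second simulation gave 0.378 to 0.357 (6%) and 0.388 to 0.352 (9%).

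**Strength.** The same gap exists for isometric strength at 3 months and return to sport. No separate magnitude was computed for it.

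**The case against.** The strongest reply is that the plan is silent rather than wrong, and that the harm depends on loss patterns nobody has observed. Much of this stands.

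- A reader might infer that the plan commits to separate tests at every visit. It does not; it names no visit. What stands is that any single-visit t-test drops patients without that visit's score.
- A reader might infer that unequal loss by itself biases the t-test. It does not, as the first row of the table shows.
- A reader might take 0.3 to 0.4 SD as the expected bias. Those values need heavy control loss with strong selection in one group only, or selection in opposite directions. Nothing in the documents points to either. With the same dependence in both groups and unequal rates, the bias is 0.05 to 0.15 SD and type I error is at most 6.0%.
- A reader might infer that the primary strength results are threatened at 2 years. No strength or functional test is listed after return to sport. The 2-year contact serves the questionnaires, a secondary aim, and the study endpoint is tied to one-year follow-up of 20 patients.
- A reader might infer that Excel rules out a better model. The plan also provides for outside statistical analysis.

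This is a self-described pilot that acknowledges sampling bias and small size, and a mixed model leaves confounding by treatment site untouched. It also cannot recover patients excluded under the 90% attendance rule, or supply 12-month and 2-year scores that are not listed for retrospective controls. These points limit what the change can achieve. They are not reasons to prefer the t-test, which needs a stronger assumption about missing data.

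**Conclusion.** The concern holds as a conditional one, and the change is a cheap improvement. The plan analyses repeatedly measured outcomes by two-group t-tests without naming a visit or a missing-data method. If loss is related to outcome and its rate or mechanism differs between groups, the bias is about 0.05 to 0.2 SD, up to about 0.4 SD in extreme patterns. If loss is unrelated to scores, it is zero. For scale, the standard error of the 2-year difference is about 0.37 to 0.40 SD at the loss rates considered, so the bias would usually be well under one standard error.

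The sizes rest on assumed loss rates, correlations and strength of selection. The risk is greatest for the questionnaires at 12 months and 2 years. Even with random loss, using earlier scores shortens the interval somewhat, by about 5 to 9% at correlations of 0.5 or more and hardly at all at 0.3.

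**What to change.** In Data Analysis, for each questionnaire and each isometric measure, replace the t-tests with one mixed model for repeated measures:

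1. **Terms:** group, visit as a category, group-by-visit, and the pre-operative score as covariate. State how a missing pre-operative score is handled.
2. **Estimation:** restricted maximum likelihood with Kenward-Roger degrees of freedom. Use an unstructured covariance: four post-operative visits need 4 × 5/2 = 10 parameters for the questionnaires, two visits need 3 for isometric strength. Name one simpler structure, such as compound symmetry, for use if the model does not converge.
3. **Patients:** all who have any post-operative value. Include consented patients whatever their attendance under the 90% rule, where data exist.
4. **Reporting:** the group difference with 95% CI at each visit, and which of these the multiplicity correction covers.
5. **Sensitivity analysis:** impute missing scores, shift them by a stated range separately in each group, and report the shift at which the conclusion changes.
6. **Retrospective controls:** limit comparisons to the measures and visits listed for them. Reconcile the figures of 14 and 20 prospective controls, because they determine whether the fallback applies.
7. **Software:** have the university collaborator fit the model in a statistical package instead of Excel.

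Measures taken at a single post-operative visit need only that visit named and a missing-data rule.

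**Cost:** analysis wording and some of the collaborator's time; no new visits or data. **Downside:** the model assumes that loss is explained by observed scores, which is why item 5 is needed, and it does nothing about confounding by treatment site.
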